16. PHARMACOKINETIC ANALYSIS

16.1. SERUM CONCENTRATION DATA

Subjects with partial data will be evaluated on a case-by-case basis to determine if sufficient data are available for reliable estimation of PK parameters. If a subject is missing both predose sample collections, their observed concentrations will be listed and summarized but not included in baseline-corrected listings or summaries.

A listing of PK blood sample collection times as well as derived sampling time deviations will be provided. Baseline-corrected DPPC serum levels will be derived by subtracting the observed levels at sample time on Day 14 from the mean baseline on Day 1 predose, if possible. If the resulting value is negative, the estimated baseline-corrected level will be set to zero (0) for purposes of reporting and subsequent analysis.

Observed and baseline-corrected serum concentrations will be summarized by treatment using

Document: Statistical Analysis Plan
Author: [REDACTED]

Version Number:
Version Date:

2.0
03APR2019

descriptive statistics. Predose and postdose concentrations of DPPC that are below the limit of quantification (BLQ) will be treated as zero for the computation of descriptive statistics.

A subject listing of all observed and baseline-corrected concentration-time data will be presented by treatment. Figures of arithmetic mean of observed and baseline-corrected concentration-time data (\pm SD, as appropriate) will be presented by treatment on linear and semi-logarithmic scales. Individual subject observed concentration-time data will be graphically presented on linear and semi-logarithmic scales.

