2.2. SECONDARY OBJECTIVES

- To evaluate if any systemic exposure of dipalmitoylphosphatidylcholine (DPPC) can be detected in serum at levels higher than endogenous DPPC levels in serum in up to 15 healthy adult volunteers who will be evaluated in the Cohort B dose (OP0210 60 mg per day) versus placebo.
- To evaluate if any systemic exposure of cholestryl palmitate (CP) can be detected in serum at levels higher than endogenous CP levels in serum in up to 15 healthy adult volunteers who will be evaluated in the Cohort B dose (OP0210 60 mg per day) versus placebo (if feasible).

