3.2. SECONDARY ENDPOINTS

- Maximum baseline adjusted serum concentration (C_{max}) of DPPC on Day 14.
- Time to maximum concentration (t_{max}) of DPPC on Day 14.
- Maximum baseline adjusted serum concentration (C_{max}) of CP on Day 14 (if feasible).
- Time to maximum concentration (t_{max}) of CP on Day 14 (if feasible).
- Additional parameters may be calculated, if appropriate.

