7.5. BASELINE

Baseline is defined as the last scheduled non-missing measurement taken prior to dosing and will

Document: Statistical Analysis Plan
Author: [REDACTED]

Version Number:
Version Date:

2.0
03APR2019

correspond to: Screening assessment for clinical laboratory; Day -1 assessment for Vital Signs; Day 1 pre-dose assessment for ECG in Cohort A, and the average of the mean triplicate ECG assessments at Day 1, 60 minutes pre-dose and Day 1, 30 minutes pre-dose for ECG in Cohort B; Screening assessment for Physical Examination; Day -1 assessment for Otoscopy, Tympanometry, and Nasal and Epipharynx Endoscopy ; and Screening assessment for University of Pennsylvania Smell Inventory Test (UPSIT) Olfactory test, and Audiology Pure Tone hearing test. However, if a subject is missing the planned baseline collection then the last non-missing evaluation prior to dosing (scheduled or unscheduled), if available, will become the baseline value.

For PK assessments, baseline serum concentration is defined as the mean of the two predose serum concentrations observed in samples collected on Day 1 prior to the first dose. If one predose sample is missing, the other Day 1 predose concentration will be used for baseline correction.

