7.7. COMMON CALCULATIONS

For quantitative measurements, change from baseline will be calculated as:

- Post-baseline Value – Baseline Value

Body Mass Index (BMI) will be calculated as:

- $BMI \text{ (kg/m}^2\text{)} = \text{weight (kg)}/\text{height (m)}^2$

Age will be calculated as:

- $\text{Age (years)} = \text{Integer value of } [(\text{Date of informed consent} - \text{date of birth} + 1)/365.25]$

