16.2. PHARMACOKINETIC PARAMETERS

For PK parameter calculations, if both Day 1 predose samples are missing, no PK parameters will be estimated for this subject. If any predose sample is BLQ, it will be assigned a numerical value of zero for PK parameter calculations and baseline calculations.

Any other BLQ concentrations will be assigned a value of zero if they precede quantifiable samples in the initial portion of the profile on Day 14. A BLQ value that occurs between quantifiable data points, especially prior to C_{max} , will be evaluated to determine if an assigned concentration of zero makes sense, or if exclusion of the data is warranted. Following C_{max} , BLQ values embedded between 2 quantifiable data points will be treated as zero when calculating PK parameters. If a BLQ value occurs at the end of the collection interval (after the last quantifiable concentration), it will be set to zero.

The following PK parameters will be estimated for serum DPPC by non-compartmental methods using actual elapsed time from dosing.

C_{max}	Maximum baseline-corrected serum concentration (μ g/mL) obtained directly from the baseline-concentration versus time data.
t_{max}	Time of maximum baseline-corrected serum concentration (h), obtained directly from the observed baseline-concentration versus time data.

A subject listing of individual PK parameters will be provided. Pharmacokinetic parameters will be summarized by treatment using descriptive statistics.

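### As worded, the SAP's DPPC baseline correction is baseline minus observed, floored at zero, so a rise in serum DPPC becomes zero

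*SAP*

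**What the plan says.** SAP 7.5 sets the PK baseline: "baseline serum concentration is defined as the mean of the two predose serum concentrations" taken on Day 1 before the first dose. SAP 16.1 then states that baseline-corrected DPPC is "derived by subtracting the observed levels at sample time on Day 14 from the mean baseline on Day 1 predose", and continues: "If the resulting value is negative, the estimated baseline-corrected level will be set to zero (0) for purposes of reporting and subsequent analysis".

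SAP 16.2 takes Cmax and tmax from the corrected values; Cmax is the "Maximum baseline-corrected serum concentration". These are the DPPC secondary endpoints of SAP 3.2 ("Maximum baseline adjusted serum concentration" on Day 14, and its time). The objective in SAP 2.2 asks whether systemic DPPC "can be detected in serum at levels higher than endogenous DPPC levels in serum".

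Elsewhere in the same SAP, section 7.7 defines change from baseline for quantitative measurements as "Post-baseline Value – Baseline Value".

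**The concern.** Subtracting X from Y gives Y − X, so the SAP 16.1 sentence instructs baseline − observed. The floor then removes every negative result, and the negative results are the samples in which DPPC rose. What survives is any fall below baseline, which would be reported as a positive baseline-corrected concentration.

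Followed as written, Cmax is the largest drop below baseline and tmax is the time of that drop. Both DPPC endpoints, and the baseline-corrected listings, tables and mean plots, would then measure the opposite of what the objective asks. SAP 4.3 records that CP cannot be quantified, so no second analyte could reveal the problem.

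**Working it through.** The documents contain no DPPC concentration, within-subject SD or expected rise, so there is no figure of theirs to reproduce. The check has three parts: the text, a worked example and a simulation. All concentrations, rises and SDs below are assumptions.

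**1. Does any other text override SAP 16.1?**

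- SAP 7.7 gives the opposite sign, but as a general rule. SAP 16.1 is the specific PK rule, and a programmer would follow it.
- SAP 16.2 does not settle the direction. Each definition opens by naming the baseline-corrected concentration, but where it names the source data it leaves out the word corrected. The tmax definition also calls those data observed.
- Protocol 8.5.3 and Table 6 refer only to baseline-adjusted concentrations and give no formula.
- SAP 4.3, the list of changes from the protocol, covers only CP.

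Nothing overrides the sentence.

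**2. Worked example** (baseline 100, arbitrary units)

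- As written: corrected = max(baseline − observed, 0)
- Intended direction: corrected = max(observed − baseline, 0)

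The times are the five Day 14 nominal times in SAP Appendix 1.

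| Day 14 time (min) | −30 | 5 | 20 | 35 | 50 | Cmax | tmax |
|---|---|---|---|---|---|---|---|
| Observed, rise | 110 | 130 | 150 | 140 | 125 | | |
| As written | 0 | 0 | 0 | 0 | 0 | 0 | undefined |
| Intended | 10 | 30 | 50 | 40 | 25 | 50 | 20 |
| Observed, fall | 95 | 90 | 80 | 85 | 92 | | |
| As written | 5 | 10 | 20 | 15 | 8 | 20 | 20 |
| Intended | 0 | 0 | 0 | 0 | 0 | 0 | undefined |

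At 20 minutes in the rise, the as-written value is 100 − 150 = −50, set to 0; the intended value is 150 − 100 = 50. A peak of 1000, ten times baseline, also gives an as-written Cmax of 0.

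**3. Simulation with noise**

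Model: independent normal within-subject noise of SD s, baseline the mean of two samples, and Cmax the maximum over four post-dose samples.

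| True rise | As-written Cmax exactly 0 |
|---|---|
| 0.5s | 30% |
| 1s | 49% |
| 2s | 84% |
| 3s | 97% |
| 5s | 100% (rounded) |

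At a rise of 2s the mean Cmax is 0.09s as written and 3.03s in the intended direction. The 3.03s exceeds the true 2s because a maximum over noisy values is biased upward; with no rise at all the mean is about 1.1s in either direction. If the Day 14 predose sample is counted, making five samples, the 84% becomes 81%.

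In percentage terms, with within-subject CVs of 5%, 10% and 20%:

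| True rise | As-written Cmax exactly 0, by CV (5% / 10% / 20%) |
|---|---|
| 20% | 99% / 76% / 42% |
| 50% | 100% / 99.5% / 78% |
| 100% | 100% / 100% / 96% |

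In the intended direction, zeros occur in at most about 2% of subjects in all of these settings.

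**4. Side effect.** SAP 7.1 plans geometric means for PK parameters where applicable. A geometric mean cannot be computed over values that include zero, so this summary would also fail in the cases where DPPC rose.

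**The case against.** The strongest reply is that the intent is plain and the signal would not be lost. The objective is levels above endogenous, SAP 7.7 has the right sign, and a zero floor makes sense only for observed minus baseline. A clinical pharmacokineticist derives the parameters and would probably notice. SAP 16.1 also requires observed concentrations to be listed, summarized and plotted, including by subject, so a rise would show beside an all-zero corrected table. No hypothesis is tested, so no decision rule turns a zero Cmax into a formal conclusion. The endpoints are secondary or exploratory, confined to Cohort B, and the protocol itself doubts the relevance of systemic levels for a locally acting product. Finally, the percentages depend on assumed rises and SDs.

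Much of this stands. It is very likely a drafting slip, and the documents do not show how it was programmed. The damage is limited to the baseline-corrected outputs and to Cmax and tmax; it does not extend to everything the trial says about exposure. Safety analyses and the escalation review are untouched. Smaller assumed rises or a fifth sample change the size of the error.

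None of it makes the sentence right. Programmed as written, both endpoints are wrong. Programmed sensibly, the analysis departs from the SAP without a record.

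**Conclusion.** The SAP 16.1 rule is wrong as written and must be corrected. The direction of the error follows from the text alone and needs no assumption: every Day 14 sample above baseline is set to zero, and every sample below it is reported as a positive value. The size depends on the unknown rise relative to within-subject noise. Under the four-sample model, the share of subjects with a true rise whose Cmax is exactly zero runs from about 30% at 0.5 SD to 84% at 2 SD and 97% at 3 SD. Where Cmax is not zero, it reflects chance dips below baseline and not exposure. The effect on reported results is conditional on literal programming, and the observed-concentration outputs are unaffected.

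**What to change.** In SAP 16.1, replace the derivation with: Baseline-corrected DPPC = observed Day 14 concentration minus the mean of the Day 1 predose concentrations. The rule that sets negative results to zero can stay, since it then works as intended.

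In SAP 16.2, state in both definitions that Cmax and tmax come from the baseline-corrected concentration versus time profile, and remove the word observed from the tmax definition.

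Check the programming specification and the derived dataset against the corrected formula.

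The cost is one sentence, two small wording edits and a program check. Data collection does not change.

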16.2. PHARMACOKINETIC PARAMETERS

For PK parameter calculations, if both Day 1 predose samples are missing, no PK parameters will be estimated for this subject. If any predose sample is BLQ, it will be assigned a numerical value of zero for PK parameter calculations and baseline calculations.

Any other BLQ concentrations will be assigned a value of zero if they precede quantifiable samples in the initial portion of the profile on Day 14. A BLQ value that occurs between quantifiable data points, especially prior to C_{max} , will be evaluated to determine if an assigned concentration of zero makes sense, or if exclusion of the data is warranted. Following C_{max} , BLQ values embedded between 2 quantifiable data points will be treated as zero when calculating PK parameters. If a BLQ value occurs at the end of the collection interval (after the last quantifiable concentration), it will be set to zero.

The following PK parameters will be estimated for serum DPPC by non-compartmental methods using actual elapsed time from dosing.

C_{max}	Maximum baseline-corrected serum concentration (μ g/mL) obtained directly from the baseline-concentration versus time data.
t_{max}	Time of maximum baseline-corrected serum concentration (h), obtained directly from the observed baseline-concentration versus time data.

A subject listing of individual PK parameters will be provided. Pharmacokinetic parameters will be summarized by treatment using descriptive statistics.

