2.0 INTRODUCTION

2.1 Study Rationale

OP0201 metered dose inhaler (MDI) (referred herein simply as OP0201) is a novel, intranasal drug-device surfactant product being developed by Novus Therapeutics, Inc., for the treatment and prevention of otitis media (OM). To date, there is no drug product that has been approved to treat or prevent OM.

OP0201 is comprised of a 20:1 fixed combination of dipalmitoylphosphatidylcholine (DPPC; a phospholipid surfactant) and cholestryl palmitate (CP; a neutral phospholipid spreading agent) suspended in propellant (HFA 134a). There are no other ingredients (ie, no excipients, no fillers) in the formulation other than the active ingredients and the propellant. None of these ingredients contain any animal or human derivatives. Both DPPC and CP are highly endogenous surfactants in humans, including the Eustachian tube (ET), nasopharynx, and respiratory system.

The drug product will be delivered as a local treatment through each nostril using a metered dose inhalation device. It will be sprayed directly backwards into each nostril by way of the anterior nostrils (not upwards towards the osteomeatal opening to the maxillary and ethmoid sinuses as other common intranasal products) towards the lateral wall of the nasal cavity so that the usual nasal mucociliary clearance pathway can facilitate delivery of the drug to the ET.

This Phase 1 safety study is designed to evaluate the safety and tolerability of daily intranasal OP0201 use for 14 consecutive days in 30 healthy adults. The study will be randomized, double-blind, placebo-controlled, parallel-group, and includes a dose-escalation cohort design with evaluation of 30 mg per day (Cohort A) and 60 mg per day (Cohort B) of OP0201.

For more information about OP0201, please refer to the most recent Investigator's Brochure (IB).

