17.7. LABORATORY EVALUATIONS

Central laboratory results will be included in the reporting of this study for Hematology, Clinical Chemistry, Coagulation, and Urinalysis. Viral serology, urine drug and alcohol screening, pregnancy and FSH levels will be assessed as part of subject screening to determine eligibility. A list of laboratory assessments to be included in the outputs is included in Appendix 3 of the protocol, Table 6. Presentations will be in SI Units, as provided by the labs.

Protocol-specified clinical laboratory tests will be summarized using descriptive statistics. Clinical laboratory data collected during study conduct, which were not required per protocol, such as for special testing to further evaluate an AE, will be listed separately and not summarized.

Quantitative laboratory measurements reported as “< X”, i.e. below the lower limit of quantification (BLQ), or “> X”, i.e. above the upper limit of quantification (ULQ), will be converted to X for the purpose of quantitative summaries, but will be presented as recorded, i.e. as “< X” or “> X” in the listings.

The following summaries will be provided for laboratory data:

- Observed and change from baseline to Day 14 (for quantitative measurements).

Document: Statistical Analysis Plan
Author: [REDACTED]

Version Number: 2.0
Version Date: 03APR2019

[REDACTED]

- Incidence of abnormal values according to normal range criteria
- Shift from baseline according to normal range criteria (for quantitative measurements and categorical measurements) for Day 14.

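### SAP 16.2 sets a BLQ predose DPPC value to zero in the baseline of an endogenous compound, so about half of the natural level (one predose sample BLQ) or all of it (both BLQ) can be reported as exposure

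*SAP*

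**What the plan says.** SAP 16.2 covers Day 1 predose samples that fall below the limit of quantification: "If any predose sample is BLQ, it will be assigned a numerical value of zero for PK parameter calculations and baseline calculations". SAP 7.5 makes the baseline "the mean of the two predose serum concentrations observed in samples collected on Day 1", so a single zero enters with weight one half.

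SAP 16.1 then forms the baseline-corrected value and floors negative results at zero. SAP 16.2 takes Cmax as the largest corrected value. SAP 6.3 admits a Cohort B subject to the PK set only with at least one quantifiable postdose DPPC value.

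The documents treat DPPC as naturally present. Protocol 2.1 says "Both DPPC and CP are highly endogenous surfactants in humans", and the secondary objective (SAP 2.2) asks whether serum DPPC rises above its endogenous level. For safety laboratory results reported as below X, SAP 17.7 uses another convention: they "will be converted to X for the purpose of quantitative summaries".

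**The concern.** For a drug foreign to the body, zero is a natural value for an undetected predose sample. For an endogenous compound the result is censored: the true value is somewhere between zero and the LLOQ, and zero is the lowest substitute available. In an observed-minus-baseline calculation the error can go only one way, towards apparent exposure. It falls on the quantity that the secondary objective examines.

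The entry rule for the PK set adds to this. A subject with a fully BLQ baseline enters only by having a postdose value at or above the limit, so a small natural fluctuation across the limit can look like a rise from nothing. No sensitivity analysis for a BLQ baseline is planned.

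**Working it through.** **No plan figure to reproduce.** The documents give no LLOQ, no expected serum DPPC level and no variance, and the sample size has no statistical basis (SAP 8.1). Everything below is therefore on a scale where LLOQ = 1, with assumptions stated.

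**Direction of subtraction.** SAP 16.1 describes the correction as "subtracting the observed levels at sample time on Day 14 from the mean baseline on Day 1 predose", which read literally is baseline minus observed. SAP 7.7 defines change as "Post-baseline Value – Baseline Value", and taking Cmax as a maximum makes sense only in that direction. I use observed minus baseline.

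**Formula.** Baseline b = (p1 + p2)/2, with BLQ values set to s. Corrected Cmax = max(0, highest Day 14 postdose value − b). In the PK set the highest postdose value is quantifiable, so s acts on Cmax only through b. With k BLQ predose samples, moving s from 0 to 1 raises b by k/2: half an LLOQ for one BLQ sample and a full LLOQ for two.

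**Worked cases.** Postdose values are constant at 1.05, a quantifiable predose sample also reads 1.05, and there is no drug effect.

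| Day 1 predose samples | Baseline (BLQ = 0) | Corrected Cmax | Share of 1.05 |
|---|---|---|---|
| Both BLQ | 0 | 1.05 − 0 = 1.05 | 100% |
| One BLQ | (0 + 1.05)/2 = 0.525 | 1.05 − 0.525 = 0.525 | 50% |
| None BLQ | 1.05 | 0 | 0% |

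With both BLQ, a substitute of LLOQ/2 gives 1.05 − 0.5 = 0.55, and LLOQ gives 1.05 − 1 = 0.05. In the literal SAP 16.1 direction, all three cases in the table come to zero after flooring.

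**Simulation 1: subjects differ in natural level.** Assumptions: no exposure, lognormal levels, between-subject CV 40%, within-subject CV 15%, two predose and four postdose samples, SAP 16.1 floor applied, 400,000 subjects. Share with an apparent rise of at least 0.5 LLOQ:

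| Median natural level | Zero rule | True values |
|---|---|---|
| 1 × LLOQ | 27% | 6% |
| 1.5 × LLOQ | 29% | 17.5% |
| 2 × LLOQ | 33% | 29% |
| 3 × LLOQ | 46.0% | 45.6% |

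The true-value column rises because a fixed 0.5 LLOQ becomes small relative to the natural level. The effect of the rule is the gap between the columns. At a median of 1 × LLOQ, mean corrected Cmax is 0.30 LLOQ under the zero rule, 0.19 with true values and 0.13 with BLQ set to LLOQ. About 35% of simulated subjects there would not enter the PK set; among those who would, the shares are about 41% and 10%.

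**Simulation 2: every subject has the same natural level.** Mean corrected Cmax as a multiple of that level, at a natural level equal to the LLOQ, in subjects meeting the PK-set rule, for within-subject CV of 10%, 20% and 30%:

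| Handling of BLQ baseline | CV 10% | CV 20% | CV 30% |
|---|---|---|---|
| Zero (SAP) | 0.60 | 0.71 | 0.82 |
| LLOQ/2 | 0.34 | 0.44 | 0.55 |
| LLOQ | 0.08 | 0.18 | 0.28 |
| No censoring | 0.12 | 0.25 | 0.39 |

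Here 77–80% of subjects have at least one BLQ predose sample and 27–31% have both. At 2 × LLOQ the zero rule gives 0.11–0.36 against 0.11–0.35 without censoring. Zero and LLOQ bracket the uncensored result.

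**The case against.** The strongest objection is that the rule may never be used. No LLOQ or serum level is given, and the documents lean towards measurable baselines: Protocol 8.5.2 plans to establish endogenous concentrations from placebo baseline samples, and SAP 4.3 drops CP because its assay was not feasible while DPPC is kept. This stands as a limit on materiality. It does not defend the rule, which is written for exactly the case where a BLQ value occurs.

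A reader might infer that any subject near the assay limit has the whole natural level reported as exposure. The documents do not support that. It needs both Day 1 samples BLQ and a quantifiable postdose value. Even with the natural level at the LLOQ, both are BLQ in only about three subjects in ten in the second simulation.

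It is also fair to say that the LLOQ as sole substitute has its own bias. It is the highest possible value, gives a smaller mean rise than the true values (0.13 against 0.19 LLOQ), and can hide up to one LLOQ of real exposure. In a safety study, erring towards declaring exposure can be defended. SAP 17.7 concerns laboratory summaries and sets no binding precedent for PK. These points count against replacing zero with LLOQ alone; they do not support zero alone.

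Finally, the artefact could be traced. Observed concentrations are listed, summarized and plotted, and the analysis is descriptive with 12 planned active subjects in Cohort B. A placebo profile would show the same artefact, and the SAP 6.3 PK set includes placebo. But Protocol 8.5.2 says that postdose placebo samples will not be analyzed, so that check is uncertain.

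**Conclusion.** The point holds as a conditional one. Whenever a Day 1 predose DPPC value is BLQ, SAP 16.2 understates the baseline of an endogenous compound, by up to half an LLOQ for one such sample and up to a full LLOQ for two. With observed-minus-baseline correction this biases corrected Cmax upward.

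Under the assumed CVs the effect is large when the typical level is at the LLOQ (27% against 6% of subjects), modest at twice the LLOQ (33% against 29%) and negligible from about three times. These figures also rest on lognormal, independent samples.

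A reader might go further and infer that this trial will report false exposure. That cannot be shown without the LLOQ and the serum level. Nor is all of the apparent rise due to the rule: taking the maximum of floored differences produces some rise even with true values (mean 0.19 LLOQ at a median equal to the LLOQ), and that part remains under any BLQ rule.

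The upward bias also presupposes that SAP 16.1 is put in the SAP 7.7 direction. As printed, a zero baseline would force the corrected value to zero and hide exposure instead. Severity is low, but so is the cost of repair.

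**What to change.** - Correct SAP 16.1 to state observed Day 14 level minus Day 1 baseline, in line with SAP 7.7.
- State the DPPC assay's LLOQ in the SAP.
- For baseline-corrected DPPC, apply one non-zero substitute, for example LLOQ/2, to BLQ values in both the Day 1 baseline and the Day 14 samples.
- Flag every subject with a BLQ baseline sample.
- Report corrected Cmax with BLQ set to zero and to the LLOQ as bounds, and conclude that DPPC exceeds endogenous levels only if this holds at the LLOQ bound.

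The cost is a few SAP sentences and a little more programming. In flagged subjects the LLOQ bound can understate true exposure by up to one LLOQ, which is why both bounds should be shown. If no value is BLQ, the change in substitution has no effect on the results.

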8.5.3 Calculation of Derivation of Pharmacokinetic Variables

Pharmacokinetic parameters will be derived using noncompartmental methods with Phoenix[®] WinNonlin[®] Version 6.4 or higher (Certata, L.P. Princeton, New Jersey, US) and/or SAS[®] Version 9.2 or higher (SAS Institute, Inc., Cary, North Carolina, US). Actual elapsed time from

dosing and baseline adjusted DPPC and CP concentrations will be used for the final serum PK parameter calculations.

Serum Pharmacokinetic Parameters

The PK parameters in [Table 6](#) will be determined for serum DPPC and CP on Day 14, when possible.

Table 6 Serum Blood Pharmacokinetic Parameters

Pharmacokinetic Parameter	Definition
C_{\max}	Maximum concentration, obtained directly from the baseline adjusted concentration versus time data.
t_{\max}	Time to C_{\max} .

Additional serum parameters may be calculated if deemed appropriate.

Drug concentration information that may unblind the study will not be reported to the study center or study personnel until the study has been unblinded.

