- q Study subjects need to be trained on study treatment administration on Day -1 or on Day 1, prior to the first dose.
- r Study treatment dosing recommendation: the first dose at 9:00 am, second dose at 16:00 pm and the third dose at 23:00 pm.

- s PK sample timing Cohort B only: Day 1: 30 and 60 minutes prior to the first dose, Day 14: 30 minutes prior to the last dose and 5, 20, 35, 50 minutes following the last dose on Day 14. The 5-minute PK sample should be collected within ± 2 minutes of the scheduled time and the 20-minute PK sample should be collected within $+5$ minutes of the scheduled time. All other PK samples should be collected within ± 5 minutes of the scheduled time.
- t To be completed before discharge from the study center on the morning of Day 15 (See Protocol Appendix 7 for an example).
- u This assessment is needed only if subjects discontinue the study prior to completing the questionnaire on Day 15.

Document: Statistical Analysis Plan
Author: [REDACTED]

Version Number: 2.0
Version Date: 03APR2019

[REDACTED]
[REDACTED]

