PRESENTATION OF NOMINAL TIMES

For PK outputs, nominal times will be represented as follows and in that order:

Analyte	Cohort	Nominal Timepoints
DPPC	B	Day 1: 60 mins Predose, and 30 mins Predose; Day 14: 30 mins Predose, 5 mins, 20 mins, 35 mins, 50 mins

LISTINGS

All listings will be ordered by the following (unless otherwise indicated in the template):

- Cohort
- Unique Subject ID

- Study Day
- Assessment date and time

Document: Statistical Analysis Plan
Author: [REDACTED]

Version Number:
Version Date:

2.0
03APR2019

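### Baseline-corrected DPPC Cmax is a maximum minus a mean, so it is positive on average with no exposure and, read alone against zero, cannot show DPPC above the endogenous level

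*SAP*

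**What the plan says.** The secondary objective in SAP 2.2 is to learn whether systemic DPPC exposure "can be detected in serum at levels higher than endogenous DPPC levels in serum in up to 15 healthy adult volunteers" in Cohort B, versus placebo. The endpoint in SAP 3.2 is "Maximum baseline adjusted serum concentration (C_{max}) of DPPC on Day 14", with its tmax.

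Protocol 8.5.3, Table 6, defines Cmax as "Maximum concentration, obtained directly from the baseline adjusted concentration versus time data". SAP 16.2 has the same definition in slightly garbled form: "obtained directly from the baseline-concentration versus time data". SAP 7.5 sets the baseline as "the mean of the two predose serum concentrations observed in samples collected on Day 1 prior to the first dose".

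The Day 14 sampling times in SAP 4.2 are "Day 14: 30 minutes prior to the last dose and 5, 20, 35, 50 minutes following the last dose on Day 14". SAP Appendix 1 lists all five together for PK output: "Day 14: 30 mins Predose, 5 mins, 20 mins, 35 mins, 50 mins". Neither Table 6 nor SAP 16.2 says that the Day 14 predose sample is left out of Cmax and tmax.

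SAP 16.1 sets negative corrected values to zero. SAP 16.2 summarizes the parameters descriptively by treatment, with no threshold, confidence interval or between-arm contrast. SAP 6.3 admits Cohort B placebo subjects to the PK set. Protocol 9.3 limits that set to subjects given OP0201, and Protocol 8.5.2 says that post-dose placebo samples will not be assayed. SAP 4.3 does not list this difference as a change from the protocol.

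**The concern.** For a drug that is absent before dosing, taking a maximum does little harm. DPPC is present at all times, so every Day 14 sample is the endogenous level plus noise plus any absorbed drug. Picking the largest of several such values and subtracting an average gives a positive result from selection alone. It would come with a tmax that looks like an absorption time, although under no exposure tmax marks only where the largest random value fell.

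The objective is to separate absorbed from endogenous DPPC, and a reader will naturally compare the reported Cmax with zero. A trial with no systemic absorption would then probably report a positive mean Cmax that could be taken for exposure. Repairing SAP 16.1 alone (direction of subtraction, zero floor) would not remove this.

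**Working it through.** The documents state no expected Cmax, power or DPPC variability, so there is no planned figure to reproduce.

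**Inputs from the documents**
- Day 14 samples: k = 4 post-dose, or k = 5 if the predose sample counts (SAP 4.2 and Appendix 1).
- Baseline: mean of 2 Day 1 predose samples (SAP 7.5).
- Cohort B: 12 OP0201 and 3 placebo (SAP 4.1, Table 1).

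**Assumptions**
- Normal errors with within-day SD s.
- Independent day effects with SD 0 to 2 s.
- Subtraction taken as observed minus baseline, with no floor.

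**Step 1: bias with no exposure.** Cmax = max(Y1, ..., Yk) - (B1 + B2)/2. The baseline mean and the day effects average out, so E[Cmax] = s × E[maximum of k standard normals]. By simulation (1,000,000 or more subjects per setting) this is 1.03 s for k = 4 and 1.16 s for k = 5. Day effects leave the expectation unchanged.

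**Step 2: how often it is positive with no exposure.**

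| Day-to-day SD | Subjects above 0, k=4 | k=5 | Mean of 12 above 0, k=4 | k=5 |
|---|---|---|---|---|
| 0 | 85% | 89% | >99.9% | >99.9% |
| 0.5 s | 80% | 83% | 99.8% | >99.9% |
| 1 s | 72% | 75% | 98% | 99% |
| 2 s | 63% | 65% | 88% | 91% |

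**Step 3: serial correlation.** The post-dose samples are 15 minutes apart, so their errors may not be independent. With first-order correlation of 0.5 or 0.8 between successive samples, the k = 4 bias falls from 1.03 s to 0.82 s or 0.55 s.

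**Step 4: scale (illustration only).** Bias as a percentage of the endogenous level = 1.03 × CV or 1.16 × CV, where CV is an assumed independent within-day CV. At 5%, 10% and 20% this gives about 5%, 10% and 21% (k = 4), or 6%, 12% and 23% (k = 5).

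**Step 5: the floor as planned.** Setting negative values to zero raises the mean to 1.10 s (k = 4) or 1.22 s (k = 5) with no day effect.

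**Step 6: tmax.** With independent errors and k = 5, each sample is equally likely to be the largest, so 1 in 5 unexposed subjects would have a tmax of about -0.50 h.

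**Step 7: placebo as reference.** Comparing Cmax between 12 and 3 subjects with the floor kept, the mean null difference is about zero (-0.003 to 0.006 s), so the bias cancels. Precision is poor. A two-sided 5% t-test (my assumption; none is planned) has 28-30% power for a true rise of 1 s without day effects, and 9-10% with a day-effect SD of s. For a rise of 2 s the figures are 81-83% and 33-34%.

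**The case against.** A reader might infer that Cmax is always positive, that the group mean is all but certain to be positive, or that the trial cannot detect exposure at all. The documents support none of these. Positivity is a property of the average: 11-37% of unexposed subjects would have an unfloored Cmax at or below zero in the settings above. The near-certain positive group mean needs little or no day-to-day variation. Serial correlation shrinks the bias, and the documents say nothing about either.

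Nor does a placebo group fail because it carries the same bias. Equal bias in both arms cancels in the difference. The difficulties are that no difference is planned, that there are at most 3 placebo subjects in Cohort B, and that Protocol 8.5.2 would leave their post-dose samples unassayed.

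Cmax is also not the only planned PK output. SAP 16.1 provides observed and corrected concentration summaries, mean profiles and individual plots, and Protocol 9.4.2 summarizes by time point. The observed time-point means have no selection bias. This objection stands and limits the harm, but those summaries are not the named endpoint, and the corrected ones carry the zero floor.

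Finally, the endpoint is secondary or exploratory in a Phase 1 safety study without hypotheses, and Protocol 4.3 doubts that systemic levels matter. That keeps the point modest. It does not make the endpoint answer its objective.

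**Conclusion.** The point holds for Cmax in the OP0201 group read alone against zero: it cannot show DPPC above the endogenous level, and tmax may only locate noise. The no-exposure bias is about 1.03 s or 1.16 s with independent errors, and 0.82 s or 0.55 s at serial correlations of 0.5 or 0.8 (k = 4). With day-to-day SD from 0 to 2 s, about 63-89% of unexposed subjects and about 88% to over 99.9% of group means of 12 would lie above zero. All sizes rest on assumed normal errors and assumed variance ratios; only the direction of the bias follows from the definition. The point does not extend to a placebo-controlled difference, nor to the observed concentration summaries. It should be settled before unblinding.

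**What to change.** 1. In SAP 16.2 add a supportive exposure measure, recorded in SAP 4.3 as a change from the protocol: the mean of the four Day 14 post-dose samples minus the mean of the two Day 1 predose samples, unfloored, with a 95% CI by treatment. Cmax stays as the protocol endpoint.
2. Restrict Cmax and tmax to samples taken after the last dose.
3. State that Cmax and tmax are descriptive and that Cmax is not interpretable against zero.
4. Reconcile Protocol 8.5.2 with SAP 6.3. Where placebo post-dose values exist, report the same measure for placebo and the OP0201-minus-placebo difference with a CI.

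Item 4 matters because the new measure averages zero without exposure only if nothing else shifts between Day 1 and Day 14. Baseline precedes the 9:00 dose, while the Day 14 samples surround the 23:00 dose after two weeks of residency. A time-of-day or residency shift would stay in the within-group change; a placebo difference removes it if it is common to both arms.

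Reporting tmax only when the raw Day 14 post-dose maximum exceeds the subject's highest Day 1 value would not help. With six exchangeable values it passes 4/6 = 67% of unexposed subjects.

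The cost is SAP wording and one derived variable from samples already scheduled, plus assay of the Cohort B placebo post-dose samples if that is how item 4 is resolved. There are two drawbacks. A brief peak caught in one sample is diluted in the average, which is a reason to keep Cmax. And the contrast with 3 placebo subjects is imprecise: the SE of the difference in mean change is s × √(1/4 + 1/2) × √(1/12 + 1/3) = 0.56 s without day effects, and s × √(0.75 + 2) × √(1/12 + 1/3) = 1.07 s with a day-effect SD of s.
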